## **Response to PPI Comments:**

We value the insights provided by our Patient and Public Involvement (PPI) advisors and have incorporated their feedback to enhance the credibility and effectiveness of our RCT protocol. Below are the key adjustments made in response to their valuable input:

#### 1. Emphasized Importance of Commitment:

We have highlighted the significance of commitment on the ReFresh page, encouraging participants to view the program as a transformative journey towards managing fatigue effectively and achieving optimal well-being. The language has been revised to underscore the need for consistent engagement to reap the benefits of the program.

## 2. Addressed Concerns Regarding Vivid Dreams:

Feedback regarding vivid dreams has been carefully considered, and appropriate measures have been implemented to address this concern within the protocol.

#### 3. Enhanced Accessibility for Devices:

To ensure inclusivity and accessibility, the program has been optimized for various devices, making it more user-friendly and accessible across different platforms.

#### 4. Simplified Language in the Information Sheet:

The language used in the information sheet has been simplified to enhance clarity and comprehension for all participants, aligning with the feedback provided by our PPI advisors.

#### 5. Adjusted Exercise Feedback Frequency:

In response to feedback, exercise guidance has been revised to encourage participants to engage in routines more frequently, surpassing the previous recommendation of three times a week.

These adjustments reflect our commitment to integrating diverse perspectives and ensuring that the ReFresh program meets the needs of our participants effectively. The revised RCT protocol now incorporates these modifications, reinforcing the program's credibility and efficacy.

# Online Fatigue Management Program Content

We will recommend participants access one module per week i.e. six modules over six weeks and undertake at least three 30-minute sessions of exercise per week.

# Modules of Fatigue Management

## Based on Thomas et al 2013

Session	Title	Content	Homework
1	Introducing fatigue	General introduction; expectations; types of fatigue; contributing factors, conceptual model of fatigue in PwP	Activity/fatigue diary Exercise
2	Opening an "energy account"	Rest – functions; barriers, techniques; relaxation types and techniques; diaphragmatic breathing exercise; sleep hygiene	Rest/activity/sleep planner Exercise
3	Budgeting energy and smartening up goals	Types of activity; balancing activity and rest; moderating activity using the toolbox; lifestyle factors; goal setting	S.M.A.R.T. goal setting exercise Exercise
4	The stress response; Introducing the	The stress response (fight-or- flight); ways of coping with stress; introducing the cognitive behavioural model	Unhelpful thoughts (related to fatigue) diary Exercise

Session	Title	Content	Homework
	cognitive behavioural model		
5	Putting unhelpful thoughts on trial	Unhelpful thought patterns; challenging unhelpful thoughts; levels of belief	Thought challenge sheet Exercise
6	Recapping and taking the programme forward	Revisiting expectations; introducing the 'forcefield'; group activity to revisit themes of the programme; rationale of 'Keeping on Track' planner	'Keeping on Track' planner Exercise

## 1. Introducing fatigue

General introduction; expectations; types of fatigue; contributing factors, conceptual model of fatigue in PwP, Fatigue is a complex and subjective phenomenon that encompasses physical, mental, and emotional exhaustion (Armstrong and Okun 2020). Fatigue is considered pathological when it becomes abnormally severe restricting one's ability to operate optimally and independently. Research estimates that up to 50% of patients experience the symptom, which significantly impact patients' quality of life (Herlofson and Kluger 2017; Armstrong and Okun 2020). It is a common non-motor symptom experienced as significant loss of energy. PD patients experiencing fatigue show decreased ability to perform normal activities and tasks, and feelings of tiredness, weakness, and tiredness (Herlofson and Kluger 2017). The etiology of fatigue in PD is unknown and fatigue presentation can sometimes be mistaken with fatigability or a feeling present at rest. Fatigability is induced by activity (Friedman et al. 2007).

The causes and triggers of the fatigue are complex and may include a combination of medical, psychological, and environmental factors. They include poor sleep (Lin et al. 2021), busy day especially for older adults (Pauletti et al. 2023), emotions and over-heating (Friedman et al. 2007). One study (Armstrong and Okun 2020) linked fatigue in PD to

psychological distress and other behavioural disorders like anxiety and apathy that are intrinsic to PD. Research has explored the underlying neurodegenerative process of PD a trigger of fatigue (Zafar and Yaddanapudi 2022). The degeneration of dopamine-producing neurons in the brain can result in motor symptoms such as tremors, rigidity, and bradykinesia, which can be physically and mentally exhausting. It can also lead to changes in the brain's regulatory systems, which can disrupt sleep and contribute to fatigue.

Medications such as levodopa, can cause fluctuations in motor function resulting in fatigue (Pauletti et al. 2023; Lin et al. 2021; Friedman et al. 2007). Other medications, such as dopaminergic agonists, can cause side effects such as somnolence, which can result in increased feelings of fatigue. Lifestyle factors can also play a role in fatigue in people with PD (DeMaagd and Philip 2015: p.524). Poor sleep hygiene, such as irregular sleep patterns, can contribute to fatigue and make it more difficult for people with PD to manage their symptoms. Sleep disturbances, such as insomnia or sleep apnea, depression, anxiety, reduced motivation and decreased physical and cognitive functioning (Herlofson and Kluger 2017). A sedentary lifestyle can also lead to decreased physical activity and increased feelings of fatigue.

Promotion of exercise (see below for details of exercise program). This will be promoted within every module of the ReFresh Program.

Assessment of acceptability (see outcomes)

#### 2. Opening an energy account

Rest – functions; barriers, techniques; relaxation types and techniques; diaphragmatic breathing exercise; sleep hygiene. Boom and bust cycles. Avoidance. Knowing when to stop – and how to take proper rest. Energy diary – identifying the energy load of activities. Supply and demand. Planning – off loading, prioritising, identifying what to stop doing. Pacing overall energy load of activities in a day, pacing to do more, time limits, chunking. Planned crash landings (for important events) – including pre and post event resting.

Existing literature highlights the positive impact of adopting good sleep hygiene on alleviating fatigue (Newland et al., 2019; Orlandi et al., 2012). However, it is crucial to

ensure that sleep patterns align with the circadian cycle, as disruptions in this regard can actually worsen fatigue (Van Hilten et al., 1993).

Night-time frequency and urgency – how to manage, maintaining night-time mobility, cueing, lighting, grab rails.

Promotion of exercise (see below for details of exercise program). This will be promoted within every module of the ReFresh Program.

Assessment of acceptability (see outcomes)

## 3. Budgeting energy and smartening up goals

Types of activity; balancing activity and rest; moderating activity using the toolbox; lifestyle factors; goal setting.

Promotion of exercise (see below for details of exercise program). This will be promoted within every module of the ReFresh Program.

Assessment of acceptability (see outcomes)

## 4. The stress response; Introducing the cognitive behavioural model.

The stress response (fight-or-flight); ways of coping with stress; introducing the cognitive behavioural model.

Promotion of exercise (see below for details of exercise program). This will be promoted within every module of the ReFresh Program.

Assessment of acceptability (see outcomes)

## 5. Putting unhelpful thoughts on trial

Unhelpful thought patterns; challenging unhelpful thoughts; levels of belief

Discussion of poor attitudes to disability – particularly invisible symptoms such as fatigue. Informed by social model, CBT and motivational interviewing tools.

Promotion of exercise (see below for details of exercise program). This will be promoted within every module of the ReFresh Program.

Assessment of acceptability (see outcomes)

## 6. Recapping and taking the programme forward

Revisiting expectations; introducing the 'forcefield'; group activity to revisit themes of the programme; rationale of 'Keeping on Track' planner.

Promotion of exercise (see below for details of exercise program). This will be promoted within every module of the ReFresh Program.

Assessment of acceptability (see outcomes)

#### Exercise

We will recommend our participants exercise for at least 30 min three times a week (in line with Wu's recommendations 2021). We will recommend that the exercises challenge their balance as these appear to have particular benefit for improving fatigue (Abasi 2020; Ribas 2017). We will recommend that participants gently increase the intensity of their exercise programs from their current level, and in line with their disease stage, and response to the exercise program. We will provide appropriate safety information to ensure participants can partake of these exercises in their own homes safely.

We will recommend exercise programs from Parkinson's UK (all led by physiotherapists) https://www.parkinsons.org.uk/information-and-support/physical-activity-and-exercise

We will also recommend the use of WiiFit games that challenge balance (Table Tilt; Tilt City; Penguin Slide; Soccer Heading; Basic Run; Obstacle Course; Basic step) for 30-minute sessions (Ribas 2017)

We will provide participants on suggestions for other exercise activities and how they can incorporate them into their everyday activities to promote long term exercise promotion and engagement.

## **Appendix 2**

## **Email Templates**

#### 1. Emails for Allocation Decisions:

## For Participants in ReFresh Arm:

Subject: Allocation Decision: You are in the ReFresh Arm

Dear .....

Congratulations! We are pleased to inform you that you have been allocated to the ReFresh arm of our study. Thank you for your participation and commitment. Engaging fully with the program and completing the homework requested is critically important to allow us to make a fair assessment of the program.

Please find the link to access the ReFresh program below:

#### Link

We will be in touch with you in 12 weeks to provide you with the endpoint survey link and further instructions. Completing the surveys requested is critically important to allow us to properly assess the ReFresh program.

Should you have any questions or require further assistance, please do not hesitate to contact us.

Best regards,

## For Participants in Waitlist Group:

Subject: Allocation Decision: You are in the Waitlist Group

Dear ......

Congratulations! We are pleased to inform you that you have been allocated to the T the waitlist group. Thank you for your participation and commitment. Being a part of the waitlist group allows us to compare your results against the group that get immediate access to the ReFresh program. In a disease as variable as Parkinson's this is critical to allow us to determine if any differences are "real" and useful,

We will be in touch with you in 12 weeks to provide you with the endpoint survey link and further instructions. Completing the surveys requested is critically important to allow us to properly assess the ReFresh program.

We will then be in touch with you in 16 weeks where we will provide your with the link to the ReFresh online program. Your participation at this point will not be recorded.

If you have any questions or concerns, please feel free to reach out to us.

Best regards,

### 2. COPM Result Emails:

Subject: COPM Survey Results

Dear ......

We are pleased to share with you the results of your personal activity survey (Canadian Occupational Performance Measure (COPM)).

## [COPM Results]

You will need this with you when you complete the 12 week endpoint assessment as we will ask you to rate yourself against your personal activities at that time point as well.

If you would like to discuss your results or require further clarification, please do not hesitate to contact us.
Best regards,
3. Emails for 12-Week Endpoint Survey and Reminder:
For 12-Week Endpoint Survey: Subject: Endpoint Survey: 12-Week Follow-Up
Dear
It's time for the 12-week follow-up survey as part of our study. Your input is invaluable to us, and we appreciate your continued participation. All of this data is critical to our understanding of the ReFresh program.
Please click on the link below to complete the survey:
[Survey Link]
Thank you for your time and contribution.
Best regards,
For Reminder:
Subject: Reminder: 12-Week Endpoint Survey
Dear

[figure not shown]
We hope this email finds you well. Just a friendly reminder to complete the 12-week endpoint survey if you haven't already done so.
Your feedback is crucial to our study, and we greatly appreciate your participation.
Please click on the link below to access the survey:
[Survey Link]
Thank you for your cooperation.
Best regards,
4. Emails for 16-Week Waitlist Group to Access ReFresh Program:
Subject: Access to ReFresh Program: 16-Week Waitlist Group
Dear
We are pleased to inform you that you now have access to the ReFresh program as part of the 16-week waitlist group.
Please find the link to access the program below:
[Link]
Should you have any questions or need assistance, please feel free to reach out to us.
Best regards,

[figure not shown]

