#### Method

#### Design

A pilot randomised controlled trial with **two parallel comparator groups**; the ReFresh online fatigue management program versus a wait list group who will receive treatment as usual, and then access the ReFresh online course at week 14 to ensure all end point data is gathered. We will recommend participants access one **module per week** i.e. six modules over six weeks, and undertake at **least three 30 minute sessions of exercise per week**. The primary outcome will be fatigue at 12 weeks. All measures will be unblinded as it is impossible to blind participants as to whether they have accessed the web site or not.

This pilot study will check study processes (e.g., recruitment, randomisation, treatment, follow-up assessments) all run smoothly, and determine the acceptability and practicality of the ReFresh intervention. It will also appraise the feasibility and sensitivity of two fatigue measures in order to decide which measure will be the primary outcome measure in the fully powered RCT this pilot study will inform. The fatigue measures are the Parkinson's Fatigue Scale (PFS) (Baghoori 2017) and the Modified Fatigue Impact Scale (MFIS) (Fisk et al., 1994). These will be measured at baseline and 12 weeks. Once the primary measure is selected it will inform the number of participants required for a fully powered RCT.

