## Blinding

Blinding to group allocation will not be possible as participants will know whether they had access to the online fatigue management program. All assessments will be completed by participants via online surveys. The trial data will be analysed by SA who will not be blinded to allocation.

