## Canadian Occupational Performance Measure (COPM)

The COPM is a self-reported outcome measure that will be used by the ReFresh group only. This tool enables the client to identify what is meaningful for them to work on — in this context we will focus on fatigue-related goals. It encourages focussed goal setting, self-reflection, and awareness. It focuses on a person's perception of their performance and how satisfied they are with it, rather than measuring improvement in function. For a symptom as subjective as fatigue this may be a more sensitive way to measure fatigue-associated issues of importance to our participants. It is highly individualised as it focusses on the patient's personal goals. It has been used in Parkinson's disease (Gaudet 2002; Alsaeed 2021).

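### Only ReFresh participants are told to have their COPM results with them for the 12-week assessment that also yields the primary fatigue scores: an avoidable difference in measurement conditions, of unknown effect

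*Protocol*

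**What the plan says.** The Design section sets the endpoint: "The primary outcome will be fatigue at 12 weeks". It is measured with MFIS and PFS. The same section accepts that there is no blinding ("All measures will be unblinded as it is impossible to blind participants"), and the Blinding section adds: "All assessments will be completed by participants via online surveys".

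On the COPM, the Secondary measures section says: "The COPM is a self-reported outcome measure that will be used by the ReFresh group only". It adds that the measure will concentrate on goals related to fatigue.

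In Appendix 2, the COPM email opens with "We are pleased to share with you the results of your personal activity survey". After a placeholder for the results it continues "You will need this with you when you complete the 12 week endpoint assessment", and gives the reason: "as we will ask you to rate yourself against your personal activities at that time point as well".

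The waitlist allocation email says only this about the endpoint: "We will be in touch with you in 12 weeks to provide you with the endpoint survey link and further instructions". The ReFresh allocation email carries the same sentence. Appendix 2 then has one 12-week survey email, with one link, and a reminder.

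**The concern.** When the primary outcome is subjective, self-completed and unblinded, collecting it in the same way in both arms is one of the few protections left. The email attaches extra material about personal, fatigue-related goals to the endpoint occasion in one arm only. If that material affects how someone answers MFIS or PFS, the effect becomes part of the between-arm difference.

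That difference has two uses. The first aim feeds it into the sample size of the definitive trial. The Outcomes section uses the same data to decide which fatigue scale is more sensitive. The protocol describes MFIS as weighted more heavily than PFS towards fatigue's effect on activities. A reminder of chosen activities could therefore touch the two scales unequally; that last step is an inference, not something the protocol says.

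**Working it through.** The point rests on reading sections together. No figure in the protocol tests it.

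1. **Who gets the email.** The template carries no arm label. That it goes to ReFresh participants only follows from the COPM section, which is explicit.

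2. **What occasion the instruction covers.** It refers to the endpoint assessment as a whole, not to a COPM part of it. The re-rating is placed at that same time point, and Appendix 2 offers a single survey link with no separate COPM invitation. On the text, the COPM and the primary scales share one occasion.

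3. **What the other arm is told.** The two allocation emails announce the 12-week contact in identical terms. The COPM email is thus the only template that tells participants to have something with them, and it has no waitlist counterpart.

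4. **What the stated purpose needs.** Re-rating one's own activities requires the list of those activities. It does not require earlier ratings, and it does not require the list before the COPM items are reached.

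5. **What is not stated.**
   - The content of the emailed results: only a placeholder is shown.
   - The order of the scales in the 12-week survey.
   - When the COPM is first completed. Randomisation follows completion of baseline data, so a ReFresh-only COPM is either completed after allocation or completed by everyone before it. The difference at 12 weeks exists in either case.

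6. **Exposure.** The planned size is 20 + 20 = 40. The instruction reaches 20 of 20 in ReFresh and 0 of 20 in the waitlist arm.

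7. **How a shift would act.** Let Δ be the true difference in mean change and δ any shift in the ReFresh 12-week mean caused by the reminder. The estimated contrast is (ReFresh change + δ) − waitlist change = Δ + δ. Because exposure coincides with allocation, the trial's data cannot separate δ from Δ.

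8. **Size.** The protocol gives no value for δ. Its Sample size section is a rule of thumb, without an effect size, standard deviation, significance level or power. The consequence for the definitive trial cannot be calculated from the document, and no figure is offered here.

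**The case against.** The strongest reply is that the harm depends on details the protocol does not show.

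- **Content.** The emailed results may be no more than the list of chosen activities, which fits the reason the email gives. A reader might infer that participants see their earlier performance and satisfaction ratings. The word used makes that plausible, but the document does not establish it.
- **Order.** The protocol lists MFIS and PFS first and the COPM last among its named scales. If the survey follows that order, the fatigue scales are answered before the COPM. Block order is also an operational detail that a protocol need not contain. A reader might infer that participants consult their results while answering MFIS and PFS, but the email only says to have them available.
- **Mechanism.** No earlier MFIS or PFS answers are returned. The programme itself makes fatigue and goals prominent through diaries, goal setting and a planner, so one email may add little.
- **COPM anchoring.** Seeing an earlier rating could pull the COPM re-rating, but only one arm has the COPM. This cannot enter a between-arm comparison.

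All of this stands as a limit on what can be claimed, but it does not remove the point. Prominence created by the programme belongs to the intervention, whereas an instruction tied to the survey belongs to measurement, and the protocol classes the COPM as an outcome measure. The admitted lack of blinding does not cover it either: that is unavoidable, and this is not.

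**Conclusion.** The concern holds as an avoidable one-arm difference in how the primary outcome is collected. It rests on the COPM section (one arm only), the email's reference to the whole endpoint assessment, and the single survey link. It affects every ReFresh participant by plan and no waitlist participant.

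Its effect on MFIS and PFS is unknown in size and direction and may be zero. A reader might go further and conclude that the fatigue difference is inflated, or that a definitive trial sized on it would be too small by some stated percentage. The document supports neither conclusion: it contains no shift, no expected effect and no reason to prefer one direction.

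This is a worthwhile low-cost improvement, not an error or contradiction in the protocol. It is best made before data collection, because analysis cannot remove the difference afterwards.

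**What to change.** 1. State that at 12 weeks MFIS and PFS come first and in identical form in both arms. Put the COPM in a final block shown to ReFresh participants only, or in a separate survey sent after the main one is submitted. Participants who take up the hard-copy option in the Data security section need the same order, most simply with the COPM on a separate form.
2. Reword the COPM email so that participants need only their list of chosen activities, and only for the COPM part. Alternatively, pre-fill that list in the COPM block and drop the instruction.
3. Return any earlier COPM ratings after submission. This is secondary, since it protects only the uncontrolled within-arm COPM change.

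The cost is one reworded template and a reordered survey. Treatment, sample size and the set of outcomes are unchanged. The one downside is that participants wait until after the endpoint for feedback on their COPM scores.
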